### 12: ETHICS CONSIDERATIONS

The Investigator agrees that the study will be conducted in full accordance with the protocol, the principles of the ICH Guideline on GCP [32], the current revised principles of the Declaration of Helsinki [33], the National Statement on Ethical Conduct in Human Research [34], and applicable local laws and regulations of the country in which the research is conducted which provide the greatest protection to the individual.

It is the Investigator's responsibility to obtain written informed consent in compliance with ICH GCP Guidelines (Guidelines for Good Clinical Research Practice) from each subject prior to the Subject's entrance into the study or the performance of any unusual, invasive, or non-routine procedure that involves risk to the Subject. The Investigator must also explain to the Subject that participation is voluntary and that they can withdraw from the study at any time without a reason and without having to fear any loss in his/her medical care.

Prior to any study-related screening procedures being performed, the consent form will be reviewed and signed and dated by the Subject or legally authorized representatives and the person who administered the informed consent.

Subjects will have sufficient time and opportunity to clarify and resolve questions before the Subject starts the study. Furthermore, the Subject will be handed a Subject Information Sheet containing all the important information in writing. A copy of the consent form will be given to the Subject or legally authorized representatives and the original will be placed in the Investigator Study File. An entry must also be made in the Subject's source documents to confirm that informed consent was obtained prior to any study-related procedures and that the Subject received a signed copy.

The Investigator will submit the consent to the appropriate IRB/IEC for review and approval prior to the start of the study in this case Bellberry Ltd needs to approve the informed consent. If the consent form is revised during the course of the study, all active participating subjects must sign the revised form.

### 12.1 Quality Assurance

According to the ICH guidelines on GCP, the Investigator is responsible for implementing and maintaining quality assurance (QA) and quality control systems with written Standard Operating Procedures (SOPs). This is to ensure that the trial is conducted and data is generated, recorded and reported in compliance with the protocol, GCP and the applicable regulatory requirements.

Data recorded on the Subject CRFs will be subjected to a quality control review according to the investigating site's SOPs. All source document reviews will be performed against entries on the CRF and quality assurance checks will be performed to ensure that the Investigator is complying with the protocol and regulations.

All data entered in the database will be verified and cleaned by the Data Management Team. Any discrepancies will be reviewed against the CRF hard copy and corrected. After completion of the entry process, computer logic checks will be run to check for such items as inconsistent study dates and outlying laboratory values. Any necessary corrections will be made to the database and documented via addenda or audit trails.

On one or more occasions the study site may be audited by a third party or regulatory agency on behalf of the investigating site.

The Regulatory Authority or its designee, has the obligation to follow the study closely. The investigator may delegate or appoint a third party to monitor the study to ensure compliance with Good Clinical Practice (GCP). In doing so, the monitor will visit the Investigator and study facilities at periodic intervals, in addition to maintaining necessary telephone and written contact, as appropriate. The monitor will maintain a working knowledge of the study through observation, review of study records and source documentation, and discussion of the conduct of the study with the Investigator and staff.

All aspects of the study will be carefully monitored by its designee for adherence to the protocol and for compliance with applicable government regulations, current good clinical practice, and current standard operating procedures.

# 12.2 Confidentiality of Study Data

The aims, contents, and results of this study are confidential and are not to be transmitted to any third party in any form or fashion without prior approval by the Principal Investigator and the study subject.

The Investigator should keep a separate log (Subject Master List) of the assigned Subject numbers and corresponding names, addresses, telephone number and site number (if applicable).

Permission for direct access to a Subject's data will be sought in writing by the Investigator and from the Subject as part of the informed consent procedure. This gives permission to examine, analyze, verify, and reproduce any records and reports that are important to the evaluation of the study. Any party (e.g. domestic and foreign regulatory authorities, monitors and auditors) with direct access must take all reasonable precautions within the constraints of the applicable regulatory requirements to maintain the confidentiality of the subjects' identities and the Hospital Authority's proprietary information.

It is the study monitor's responsibility to verify that each Subject has consented, in writing, to direct access to their information.

### 12.2.1 Case Report Forms

CRFs are the sole property of the Investigator and should not be made available in any form to any third parties, expect for approved representatives of appropriate health, regulatory, or auditing authorities.

As part of the responsibilities assumed by participating in the study, the Investigator agrees to maintain adequate case histories for the subjects treated under this protocol. The Investigator agrees to maintain accurate CRFs and source documentation as part of the case histories.

All CRFs should be completed legibly in black ink or typed. Case report forms should never be completed in pencil.

All requested information should be entered in the CRFs. If an item is not available or is not applicable, this fact should be so indicated. Blank spaces should not be present unless otherwise directed. A correction should be made by striking through the incorrect entry with a single line and by entering the correct information adjacent to it. The correction must be initialed and dated by the person making the correction.

The Investigator must review, sign, and date each completed CRF in a timely manner.

The Investigator will allow regulatory bodies to have direct access to the source documents to verify the data reported in the CRF.

#### 12.2.2 Source Documents

Source documents are the originals of any documents used by the Investigator or institution that allow verification of the existence of the Subject and substantiate the integrity of the data collected during the trial. Source documents may include hospital records, clinical and office charts, laboratory data/information, evaluation checklists, pharmacy dispensing and other records, recorded data from automated instruments, microfiches, photographic negatives, microfilm or magnetic media and/or x-rays. Source documents should be available to support all the data recorded in the CRF.

### 13: STUDY OUTCOMES AND SIGNIFICANCE

# **13.1 Primary Endpoints**

- 1. Collection of movement and erector spinae muscle activity data in all participants.
- 2. Change over time in range of motion (ROM) in any one plane of movement compared to preintervention ROM.
- 3. A change over time in Flexion-Relaxation response in those subjects where abnormal EMG activity in flexion during baseline assessment is detected.
- 4. A change over time in maximum pain during movement score (1-10 as recorded during the inclinic ViMove assessment) for any one plane of movement.

# 13.2 Secondary Endpoints

- 1. Capture changes in low back pain levels as assessed via a Numeric Rating Scale (NRS-Pain).
- 2. Capture self-reported changes in functional status pre- and post- ThermaCare application as measured by the Oswestry Disability Index (ODI) and Roland Morris Disability Questionnaire (RMDQ) if subjects scored >3 on the NRS.
- 3. Capture impression of change from subjects post ThermaCare application using the Patient Global Impression of Change Scale (PGIC).
- 4. Observe changes in activity levels as collected by ViMove monitoring.
- 5. Correlation of Low Back Pain Classifier (LBPC) Score to ViMove Scores for flexion and extension.

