Secondary Endpoints:	
 
Capture changes in low back pain levels as assessed via a Numeric Rating Scale (NRS-Pain).
 
Capture self-reported changes in functional status pre- and post-ThermaCare application as measured by the Oswestry Disability Index (ODI) and Roland Morris Disability Questionnaire (RMDQ) if subjects scored >3 on the NRS.
 
Capture impression of change from subjects post ThermaCare application using the Patient Global Impression of Change Scale (PGIC).
 
Observe changes in activity levels as collected by ViMove monitoring.
 
Correlation of Low Back Pain Classifier (LBPC) Score to ViMove Scores for flexion and extension.
 
			

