# 3.3 Objectives

The objectives of this study are to determine if ThermaCare HeatWraps:

- 1. Affect muscle relaxation, perceived pain, and flexibility in people with low back pain.
- 2. Affect muscle relaxation, perceived pain, and flexibility in people who are actively involved in sport.
- 3. Result in changes in subjective measures of pain and disability following 8-hours of usage.
- 4. Induce changes in movement and surface muscle activity, by collecting and assessing objective movement and EMG data pre- and post- intervention.

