# 7.1.1 Inclusion Criteria for Low Back Pain Patients:

- 1. Males and Females between the age of 21-54 inclusive.
- 2. Low back pain is the primary source of pain over the last 3 weeks.
- 3. Have experienced and received treatment for muscle related low back pain over the past 3 weeks with an average score of at least 3/10 on a 10-point Numeric Rating Scale.
- 4. Must be able to communicate fluently in English.
- 5. Must provide written informed consent.
- 6. Must agree to confidentiality.

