# 7.1.2 Inclusion Criteria for Active in Sport:

- 1. Adults between the age of 21-54 inclusive, male and female.
- 2. Participate in 30 min of moderate to high intensity exercise 3 times per week.
  - Intensity is assessed using the Borg Rating of Perceived Exertion (RPE)
- 3. Must be able to communicate fluently in English.
- 4. Must provide written informed consent.
- 5. Must agree to confidentiality.

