# 8.4 Methodology

The following tasks will be conducted on the recruitment day (Day 0) for all subjects, and will be recorded in each subject's respective source documents and case report forms (CRFs):

- 1. Assessment of eligibility against inclusion and exclusion criteria
- 2. An explanation of study procedures.
- 3. Provision and obtainment of written informed consent.
- 4. Obtainment of demographic information and medical history.
- 5. Booking of Day 1 and Day 2 (based on convenience).

The main study will be conducted over 2 consecutive days for each subject.

Participants will be asked to complete each of the following - 30 minutes prior to their appointment on Day 1; the Oswestry Disability Index (ODI), a Numeric Rating Scale for Pain (NRS Pain), the Roland Morris Disability Questionnaire, and a Low Back Pain Classifier.

Both subject groups will then have a "start interview" on their allocated baseline assessment day (Day 1). This will include fitting of the ViMove movement and EMG sensors, as well as a ViMove live "pain on movement" assessment. This session will take approximately 20-30 minutes. Whilst wearing the ViMove sensors, subjects will then leave the clinic and conduct normal daily activities for a predetermined monitoring period. No ThermaCare HeatWraps are worn on Day 1. This allows a baseline assessment and allows any placebo effects from the sensors to be discounted. At the end of the monitoring session, subjects will return to the clinic to have an "end-of-day" interview. Participants will complete a Patient Global Impression of Change scale (PGIC), a repeat NRS, and will have another live ViMove assessment. Movement sensors will then be removed, and the subject will be reimbursed for that day.

The intervention day (Day 2) will have the same procedure as Day 1 (baseline), with the only difference being the additional application of ThermaCare HeatWraps during the "start interview". ThermaCare will only be applied after the live assessment, so will not be worn at the same time as the EMG sensors. Subjects will continue to wear the HeatWrap and ViMove sensors during the 8-hour daily activity monitoring period, with the wrap and sensors being removed during the end-of-day interview, prior to the end-of-day live assessment. The subject will then be reimbursed for Day 2. A schedule of events can be seen in Table 1, and a summary of the procedure can be seen in Figure 1.

Table 1. Schedule of Events

[figure not shown]

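### Secondary endpoint 2 limits ODI and RMDQ change to subjects scoring above 3 on the NRS, so Group 1 subjects who meet the entry threshold of at least 3 can fall outside it

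*Combined protocol and SAP*

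**What the plan says.** Secondary endpoint 2 appears in the Protocol Summary and again in section 13.2. Its aim is to "Capture self-reported changes in functional status pre- and post-ThermaCare application" using the ODI and RMDQ, but only "if subjects scored >3 on the NRS". Neither place says which NRS reading or visit is meant, and no reason is given for the cut.

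Four other parts of the plan bear on this:

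- **Entry, Group 1 (7.1.1 and the Summary).** Muscle-related low back pain over the past three weeks "with an average score of at least 3/10 on a 10-point Numeric Rating Scale". A subject at exactly 3 is eligible.
- **Entry, Group 2 (7.1.2).** The group is defined by exercise: "Participate in 30 min of moderate to high intensity exercise 3 times per week". There is no pain criterion.
- **Collection (8.4).** "Participants will be asked to complete each of the following - 30 minutes prior to their appointment on Day 1": the list is the ODI, the NRS, "the Roland Morris Disability Questionnaire, and a Low Back Pain Classifier". No NRS condition is attached, and Day 2 repeats the Day 1 procedure.
- **Objective 3 (3.3).** The study is to find out whether the wraps "Result in changes in subjective measures of pain and disability following 8-hours of usage". No pain level is specified.

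Section 11.2 correlates the ODI with daily activity at four time points, also without an NRS condition. It names no analysis of change in ODI or RMDQ.

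**The concern.** The entry rule includes a score of 3 and the endpoint rule excludes it. If the gate is a single-day score, an eligible subject having a good day is also excluded. The functional question in Objective 3 is then answered in a smaller group, chosen on pain, that nobody has defined. Section 8.2 describes the study as feasibility work to guide an RCT. A mean disability change and its SD from such a subset would be a poor planning input for a trial that enrols at 3 or more.

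There is a second, conditional problem. The comparison is uncontrolled and pre-post. If subjects are selected on a score taken at the same time as one of the two compared readings, random error in that score can produce apparent change with no heat effect.

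**Working it through.** **The plan's own figure.** Section 11.1 recruits 50 to keep 40 after 20% attrition: 40 / (1 − 0.20) = 50, which reproduces. This gives 20 valid subjects per group. The documents give no SD, effect size or power target, and no figure for the gated subset.

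**Inputs**

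- From the documents: n = 20 in Group 1 (11.1); entry at 3 or more (7.1.1); endpoint gate above 3 (13.2); NRS a single whole number from 0 to 10 (8.5.4).
- Assumed, none from the documents: usual pain normal with mean 4 to 5 and between-person SD 1.0 to 1.5, cut at 3 or more; day-to-day SD 1.0 to 1.5; independent errors at each reading; no treatment effect.

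**Step 1: subjects lost with a single-day gate.** Each score is the usual level plus error, rounded and held within 0 to 10. A subject is kept if the gating score is above 3. The last column is the mean NRS change when the gate is the pre-wrap score itself.

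| Mean | Between-person SD | Day-to-day SD | Excluded | Kept of 20 | Null NRS change |
|---|---|---|---|---|---|
| 4 | 1.0 | 1.0 | 27.5% | 14.5 | −0.40 |
| 4 | 1.0 | 1.5 | 32.4% | 13.5 | −0.74 |
| 4 | 1.5 | 1.0 | 22.7% | 15.5 | −0.31 |
| 4 | 1.5 | 1.5 | 27.5% | 14.5 | −0.60 |
| 5 | 1.0 | 1.0 | 12.9% | 17.4 | −0.20 |
| 5 | 1.0 | 1.5 | 19.1% | 16.2 | −0.45 |
| 5 | 1.5 | 1.0 | 13.8% | 17.2 | −0.19 |
| 5 | 1.5 | 1.5 | 18.6% | 16.3 | −0.41 |

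About 13% to 32% is excluded; 10% to 20% score exactly 3. Moving the gate to at least 3 does not remove the loss. In a separate run (mean 4 to 6, between-person SD 1.5, day-to-day SD 1.0 to 2.0) it still excludes 1.5% to 17%, against 6% to 31% with the gate above 3.

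**Step 2: precision.** The 95% half-width for a mean change, in units of the SD of change, is t(0.975, n − 1) / √n.

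- n = 20: 2.093 / 4.472 = 0.47
- n = 17.4: 2.116 / 4.171 = 0.51
- n = 13.5: 2.169 / 3.674 = 0.59

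**Step 3: regression to the mean, by choice of gate.** Among subjects with a gating score above 3, the average error in that score is positive. The average error in any other, independent reading is zero. So:

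- Gate is the pre-wrap score: NRS change −0.19 to −0.74, towards improvement.
- Gate is the post-wrap score: +0.19 to +0.74, towards worsening.
- Gate is an earlier reading that is neither of the two compared: 0.00 throughout.
- Gate is the three-week entry average, treated as the usual level: also 0.00, and only subjects at exactly 3 are lost.

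Carrying this to the ODI needs the correlation r between same-day ODI and NRS errors. The shift is r × within-person ODI SD × mean standardised NRS error in those kept. That error is 0.176 to 0.475 in the runs above. With an assumed ODI SD of 5 points and r of 0.4 to 0.6, the shift runs from 0.4 × 5 × 0.176 = 0.35 to 0.6 × 5 × 0.475 = 1.43 points. With r = 0 it is zero.

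**Step 4: is the post-wrap form scheduled?** At the end-of-day interview, 8.4 names only the PGIC and a repeat NRS. Table 1 marks unspecified questionnaires at Visits 2, 4 and 5. Section 11.2 counts four time points for the ODI. These do not agree on when, or whether, ODI and RMDQ are completed after the wrap.

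**The case against.** Restricting disability change to people in pain can be defended. The ODI measures restriction due to low back pain, so subjects with little pain have little room to improve. Group 2 has no pain criterion, and its inclusion would dilute any change. This stands for Group 2. It does not justify dropping Group 1 subjects who met the plan's own pain threshold.

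The stakes are also limited. This is a secondary endpoint in a feasibility study with no power target, and section 11.2 names no test of ODI or RMDQ change. A half-width of 0.51 to 0.59 SD instead of 0.47 SD decides nothing by itself. That stands and keeps the point moderate.

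Three stronger readings are tempting, and the documents do not support them:

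- **That the gate biases the result whichever NRS reading is used.** Step 3 shows otherwise: the bias is about zero when the gate is separate from both compared readings. Only the loss of subjects applies to every reading.
- **That the excluded subjects' data are thrown away.** Section 11.2 still uses the ODI without a gate in its correlation analysis. The RMDQ has no such second use.
- **That removing the condition certainly needs no new data.** The wording could be a rule for when to collect the forms, and 8.4 does not clearly schedule them after the wrap. On that reading the endpoint conflicts with the unconditional list in 8.4, and the same subjects are still lost.

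**Conclusion.** The point holds as an inconsistency between the functional endpoint and the entry criterion, the collection plan and Objective 3. Followed as written, the endpoint excludes eligible Group 1 subjects. With a single-day gate the loss is about 13% to 32% (13.5 to 17.4 of 20 kept), with the half-width rising from 0.47 SD to about 0.51 to 0.59 SD. With the three-week average as the gate, only those at exactly 3 are lost. In Group 2 most subjects could fall outside, but the documents give no basis for a figure.

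Regression to the mean should be reported as a possibility, not a finding. It requires a gating score taken alongside a compared ODI/RMDQ reading, and correlated same-day errors. All sizes rest on assumed SDs and independent errors between readings. The mismatch itself rests on the text alone.

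**What to change.** In the Protocol Summary and section 13.2, remove the above-3 condition for Group 1. Make the main summary of ODI and RMDQ change all Group 1 subjects with both pre-wrap and post-wrap forms. Summarise Group 2 descriptively. If the higher-pain subset is wanted, show it as a labelled subgroup, defined by a named NRS reading that is not one of the compared time points.

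Reconcile 8.4, Table 1 and 13.2 so that the post-wrap ODI and RMDQ are explicitly collected from the same subjects.

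The cost is small. Low-pain subjects have less room to improve, so the mean change may be slightly smaller. If the condition was meant as a collection rule, a few more forms are completed at Visit 5. No visit is added.

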# **13.3 Significance**

This intervention study will provide information regarding changes in movement, flexibility, and pain following the use of ThermaCare HeatWraps in subjects who either suffer from low back pain, or are moderately or highly active. Moreover, it will assess any potential relationships between changes in pain, and responses to questionnaires as well as objectively measurable changes using ViMove systems.

